3.1 Inclusion Criteria

- 3.11 Age \geq 18 years.
- 3.12 Histologically proven, unresectable distant metastatic or locally advanced Colorectal adenocarcinoma with primary tumor site from right-sided disease only (cecum, ascending colon, hepatic flexure, and transverse colon).
- 3.13 KRAS, NRAS wild type.
- 3.14 BRAF v600E wildtype.
- 3.15 Measurable disease as defined in Section 11.0.
- 3.16 ECOG Performance Status (PS) 0, 1, or 2. (Form is available on the ACCRU web site:
[REDACTED]
- 3.17 Life expectancy of \geq 3 months per estimation of treating physician.
- 3.18 The following laboratory values obtained \leq 7 days prior to randomization.

- Absolute neutrophil count (ANC) $\geq 1200/\text{mm}^3$
 - Platelet count $\geq 75,000/\text{mm}^3$
 - Hemoglobin $\geq 9.0 \text{ g/dL}$
 - Total bilirubin $\leq 1.5 \times$ upper limit of normal (ULN)
 - Alanine aminotransferase (ALT) and aspartate amino-transferase (AST) $\leq 2.5 \times$ ULN ($\leq 5 \times$ ULN for subjects with liver involvement of their cancer)
 - Serum creatinine $\leq 1.5 \times$ ULN
 - INR/PTT $\leq 1.5 \times$ ULN
- NOTE: Patients who are therapeutically treated with an agent such as warfarin or heparin will be allowed to participate provided that no prior evidence of underlying abnormality in coagulation parameters exists. Close monitoring of at least weekly evaluations will be performed until INR/PTT is stable based on a measurement that is pre-dose as defined by the local standard of care.
- Alkaline phosphatase limit $\leq 2.5 \times$ ULN ($\leq 5 \times$ ULN for patients with liver involvement of their cancer)

- 3.19a Negative serum pregnancy test done ≤ 7 days prior to randomization for women of childbearing potential only. NOTE: Post-menopausal women (defined as no menses for at least 1 year) and surgically sterilized women are not required to undergo a pregnancy test. The definition of adequate contraception will be based on the judgment of the treating physician.
- 3.19b Provide informed written consent.
- 3.19c Willing to return to enrolling institution for follow-up (during the Active Monitoring Phase of the study).
- 3.19d Disease progression on or intolerable to any of the following: fluoropyrimidine, oxaliplatin and irinotecan.
- 3.19e Able to swallow and retain oral medication.
- 3.19f Willing to provide tissue and blood samples for correlative research purposes (see Sections 6.0, 14.0 and 17.0).

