4.0 Test Schedule

4.1 Treatment with regorafenib

NOTE: Subjects should follow this test table while taking regorafenib regardless of treatment arm.

Tests and procedures	≤7 days prior to randomization	Active Monitoring Phase										End of All Treatment (within 30 days after last dose)	
		Cycle 1				Cycle 2				Prior to dosing each cycle beginning cycle 3+ (+/- 7 days)	Prior to dosing at restaging (C3 and every other cycle after) until progression (+/- 7 days)	End of Initial Treatment Mandatory Sequential Registration (if regorafenib is initial treatment) ¹²	
		Week 1 (Day 1)	Week 2 (Day 8)	Week 3 (Day 15)	Week 4 (Day 22)	Week 1 (Day 1)	Week 2 (Day 8)	Week 3 (Day 15)	Week 4 (Day 22)				
History and exam, weight, ECOG PS, blood pressure	X	X ⁷	X	X	X	X	X	X	X	X		X	X
Height	X												
Adverse event assessment	X				X				X	X		X	X
Hematology ⁵ CBC/ differential, ANC, INR/PTT ¹³	X	X ⁹				X				X			
Chemistry ⁵ SGOT (AST), alk phos, T. bili, serum creatinine, calcium, glucose, Na, K, SGPT (ALT), Mg	X	X ⁹		X		X		X		X			
Albumin ⁵	X	X ⁹			X				X				
Tumor Blood Bio-Markers (CEA)	X				X					X			
Tumor measurement ¹ (CT scan of chest, abdomen and pelvis), CT	X									X			X ⁶

component of a PET/CT, (MRI if CT is not feasible)												
ECG ⁴	X											
Serum pregnancy test ²	X	X ⁹										
Mandatory blood sample-plasma ^{10,R}		X				X						
STC1 biomarker blood collection ^R		X		X								
Mandatory tissue sample-archival tumor paraffin(see Section 17.0) ^{8, R}		X										
Patient Medication Diary (Appendix I) ³		X	X	X	X	X	X	X	X		X	X
Optional Blood sample -cfDNA Guardant 360 ^{10, 11, R}												X

1. CT scans preferred (MRI if CT is not feasible), CT component of a PET/CT, of the chest, abdomen and pelvis. Use same imaging throughout the study. Tumor measurements at baseline (≤ 28 days prior to randomization) and every 8 weeks beginning on cycle 3 day 1 prior to treatment until progression.
2. For women of childbearing potential only.
3. The diary must begin the day the patient starts taking the medication and must be completed per protocol and returned to the treating institution during each scheduled visit.
4. Performed at screening and then as needed.
5. Hematology and chemistry tests to be done prior to each cycle.
6. If patient goes off study during Cycle 1 and last CT scan was done > 28 days prior, the CT scan must be done.

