7. If baseline history, exam, weight, ECOG PS, and blood pressure were performed ≤ 3 days of C1D1, they do not need to be repeated for C1D1.
8. Receipt of archival tumor tissue is not required for study randomization and initiation of therapy. However, it is mandatory to receive the required tissue ≤ 90 days from randomization. See section 17.0.
9. If screening tests occur ≤ 7 days prior to C1D1, they do not have to be repeated prior to dosing.
10. Kits are required for this collection. Refer to Section 14.0.

11. Patients have the option to complete cfDNA testing at study completion and will be allowed to register with protocol ACCRU-GI-1611. Site will access results through the Guardant Health portal: [REDACTED]. Sites will be notified by Guardant Health via email when results are available in the portal. Refer to Section 13.7. See detailed instructions on the ACCRU website under Manuals and Forms.
12. At the time of disease progression or intolerance from initial treatment, patients will be re-registered (See 6.3) to Sequential Treatment Phase. Tests should be completed after re-registration and prior to dosing of sequential treatment. Patients will then move to the cetuximab or panitumumab ± irinotecan test table (4.2).
13. If the INR/PTT is normal at screening (and subject is not on warfarin) this test will not need to be repeated unless indicated per investigator assessment. If a subject is on warfarin with stable INR/PT at baseline, the INR/PT should be assessed on Day 5 (+/- 3 days). If value is above the therapeutic range, the dose should be modified and the assessment should be repeated weekly until it is stable.

R Research funded.

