4.2 Treatment with anti-EGFR mAb (cetuximab or panitumumab) ± irinotecan

NOTE: Subjects should follow this test table while taking anti-EGFR mAb (cetuximab or panitumumab) ± irinotecan regardless of treatment arm.

Tests and procedures	≤7 days prior to randomization	Active Monitoring Phase							
		Cycle 1		Cycle 2		Prior to dosing each cycle beginning cycle 3+ (+/- 7 days)	Prior to dosing at restaging (C3 and every other cycle after) until progression (+/- 7 days)	Day 15 (While on anti-EGFR mAb +/- irinotecan)	End of Initial Treatment Mandatory Sequential Registration (if anti-EGFR mAb +/- irinotecan is initial treatment) ¹¹
		Week 1 (Day 1)	Week 3 (Day 15)	Week 1 (Day 1)	Week 3 (Day 15)				
History and exam, weight, ECOG PS, blood pressure	X	X ⁶	X	X	X	X			X
Height	X								
Adverse event assessment	X		X		X	X			X
Hematology ⁴ : CBC/ differential, ANC, INR/PTT ¹²	X	X ⁸	X	X	X	X		X	

Chemistry ⁴ : SGOT (AST), alk phos, T. bili, serum creatinine, calcium, glucose, Na, K, SGPT (ALT), Mg	X	X ⁸	X	X	X	X		X	Ar	
Albumin ⁴	X	X ⁸		X		X				
Tumor Blood Bio-Markers (CEA)	X			X			X			
Tumor measurement ¹ (CT scan of chest, abdomen and pelvis), CT component of a PET/CT, (MRI if CT is not feasible)	X						X			X ⁵
ECG ³	X									
Serum pregnancy test ²	X	X ⁸								
Mandatory blood sample-plasma ^{9, R}		X		X						
STC1 Biomarker blood collection		X	X							
Mandatory tissue sample-archival tumor paraffin(see Section 17.0) ^{7, R}		X						X		
Optional Blood sample -cfDNA Guardant 360 ^{9,10, R}										X

1. CT scans preferred (MRI if CT is not feasible), CT component of a PET/CT, of the chest, abdomen and pelvis. Use same imaging throughout the study. Tumor measurements at baseline (≤ 28 days prior to randomization) and every 8 weeks beginning on cycle 3 day 1 prior to treatment until progression.
2. For women of childbearing potential only.

3. Performed at screening and then as needed.
4. Hematology and chemistry tests to be done prior to each cycle.
5. If patient goes off study during Cycle 1 and last CT scan was done >28 days prior, the CT scan must be done.
6. If baseline history, exam, weight, ECOG PS, and blood pressure were performed \leq 3 days of C1D1, they do not need to be repeated for C1D1.
7. Receipt of archival tumor tissue is not required for study randomization and initiation of therapy. However, it is mandatory to receive the required tissue \leq 90 days from randomization. See section 17.0.

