8. If screening tests occur \leq 7 days prior to C1D1, they do not have to be repeated prior to dosing.
9. Kits are required for this collection. Refer to Section 14.0.
10. Patients have the option to complete cfDNA testing at study completion and will be allowed to register with protocol ACCRU-GI-1611. Site will access results by creating an account at [REDACTED] Sites will be notified by Guardant Health via email when results are available in the portal. Refer to Section 13.7. See detailed instructions on the ACCRU website under Manuals and Forms.
11. At the time of disease progression or intolerance from initial treatment, patients will be re-registered (See 6.3) to Sequential Treatment Phase. Tests should be completed after re-registration and prior to dosing of sequential treatment. Patients will then move to the regorafenib test table (4.1).
12. If the INR/PTT is normal at screening (and subject is not on warfarin) this test will not need to be repeated unless indicated per investigator assessment. If a subject is on warfarin with stable INR/PT at baseline, the INR/PT should be assessed on Day 5 (+/- 3 days). If value is above the therapeutic range, the dose should be modified and the assessment should be repeated weekly until it is stable.

R Research funded.

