7.11 Planned treatment with regorafenib

Regorafenib Dose Escalation

Cycle 1:

Week	Dose ¹
1 Starting Dose	80 mg*
2	120 mg
3	160 mg
4	Off

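### Warfarin patients who are in range at the Day 5 check have no required INR while regorafenib is raised to 120 and 160 mg in cycle 1

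*Combined protocol and SAP*

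**What the plan says.** Table 4.1 applies whenever a patient is on regorafenib, in either arm. INR/PTT sits in its hematology row, which is marked at screening, cycle 1 Day 1, cycle 2 Day 1 and before each cycle from cycle 3. Days 8, 15 and 22 of cycle 1 are blank in that row. Footnote 5 agrees: "Hematology and chemistry tests to be done prior to each cycle". Chemistry is marked on cycle 1 Day 15, but that panel does not include INR.

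Footnote 13 relaxes the schedule for patients not taking warfarin: "If the INR/PTT is normal at screening (and subject is not on warfarin) this test will not need to be repeated", unless the investigator sees a reason to repeat it. For patients on warfarin the marked tests stay in force, and one check is added: "If a subject is on warfarin with stable INR/PT at baseline, the INR/PT should be assessed on Day 5 (+/- 3 days". The follow-up rule is conditional: "If value is above the therapeutic range, the dose should be modified and the assessment should be repeated weekly until it is stable". An in-range value triggers nothing.

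Section 7.11, under "Regorafenib Dose Escalation", sets 80 mg in week 1, 120 mg in week 2, 160 mg in week 3 and no drug in week 4. Section 8.1 makes each step conditional on the absence of significant drug-related toxicity.

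Two other places bear on the point. The note under 3.18 admits anticoagulated patients and says that "weekly evaluations will be performed until INR/PTT is stable based on a measurement that is pre-dose as defined by the local standard of care". Table 4.2, for anti-EGFR therapy, carries the same warfarin rule ("the INR/PT should be assessed on Day 5 (+/- 3 days"). However, its hematology row ("CBC/ differential, ANC, INR/PTT ¹²") is also marked on Day 15 of cycles 1 and 2 and in a further Day 15 column.

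**The concern.** The one on-treatment INR added for warfarin patients is timed to the lowest dose of an escalating schedule. A site that follows footnote 13 to the letter has a value that reflects essentially 80 mg. It then has no required value while the patient takes 120 and 160 mg, and the next one comes after a week off drug. The decision to escalate under 8.1 cannot take account of an INR that nobody has measured.

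Section 15.17 lists raised INR and hemorrhage among regorafenib effects above 10%. The lists for cetuximab and panitumumab in 15.27 and 15.37 include neither, yet table 4.2 has more INR checks than table 4.1. What is at stake is the safety of a probably small subgroup, not the efficacy comparison.

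**Working it through.** The plan states no figure for this interval, so there is none to reproduce. The check is a day count.

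**Inputs**
- Check window, footnote 13 of 4.1: Day 5 ± 3, i.e. Days 2 to 8.
- Cycle length, 7.1: 28 days, so cycle 2 Day 1 is Day 29.
- Visit window, 7.3: ± 3 days, so cycle 2 Day 1 can fall on Days 26 to 32.
- Dose steps, 7.11: 120 mg from Day 8, 160 mg from Day 15, last cycle 1 dose on Day 21.

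**Gap to the next required INR, if the check is in range**
- Check on Day 5: 29 − 5 = 24 days.
- Check on Day 8: 29 − 8 = 21 days. Check on Day 2: 29 − 2 = 27 days.
- With the window on cycle 2 Day 1: 26 − 8 = 18 to 32 − 2 = 30 days.

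**Doses above 80 mg inside the gap**
- Planned doses on Days 8 to 21: 21 − 8 + 1 = 14.
- All 14 fall in the gap if the check is done before the Day 8 dose; 13 do if it follows that dose.
- The step to 160 mg is always inside the gap. The step to 120 mg is inside it for checks on Days 2 to 7 and coincides with a check on Day 8.

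**Same rule under table 4.2**
- Check to Day 15: 15 − 8 = 7 to 15 − 2 = 13 days. Day 15 to cycle 2 Day 1: 29 − 15 = 14 days.

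**With INR added on Days 15 and 22 of cycle 1 in table 4.1**
- Check to Day 15: 7 to 13 days. Then 22 − 15 = 7 and 29 − 22 = 7 days.

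**How much drug remains at cycle 2 Day 1 (rough)**

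Assume once-daily dosing, linear one-compartment kinetics and full escalation. Let x = 2^(−168/h), the fraction left after 7 days at half-life h in hours. The pre-dose amount on Day 29, as a share of the 160 mg steady-state trough, is (1 − x)(x + 0.75x² + 0.5x³). The weights 0.75 and 0.5 are 120/160 and 80/160.
- Parent, h = 28 (15.15): x = 0.0156, share = 1.6%.
- M-5, h = 51 (15.15): x = 0.102, share = 9.9%.
- Longest half-lives in 15.15 (58 and 70 hours): 13% and 18%.
- Cycle 2 Day 1 three days early (Day 26): multiply by 2^(72/h), giving about 9% (parent) and 26% (M-5) at mean half-lives.
- Day 22, before the week off: (1 − x)(1 + 0.75x + 0.5x²) = 99.6% (parent) and 97.1% (M-5).

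This model leaves out metabolite formation and the enterohepatic circulation that 15.15 describes, so the figures are orders of magnitude only. They do not show that an INR at cycle 2 Day 1 would be uninformative, and the finding does not depend on them.

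**The case against.** The strongest reply is the note under 3.18. It is mandatory and asks for at least weekly checks in anticoagulated patients until INR is stable. If stable is read as stable on treatment relative to the pre-dose value, weekly checks could run into cycle 1. That reading is possible. On the plainer one, monitoring ends once a stable pre-dose value exists, which is exactly the patient footnote 13 describes. Nothing links the two texts, so 3.18 does not clearly fill the gap.

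Sections 7.0 and 9.6 also send sites to the package inserts, and local anticoagulation care may add tests. Either could close the gap in practice. The inserts cannot be seen here, and a warfarin-specific schedule should not depend on them.

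The Day 15 INR in table 4.2 may be there only because it travels with the blood count before an infusion. That is fair: the contrast shows an inconsistency, not a deliberate safeguard left out of table 4.1.

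The subgroup is probably small. Section 3.28 excludes thrombotic or embolic events within 6 months, 3.25 excludes arrhythmias that need anti-arrhythmic drugs, and total planned accrual is 72. The toxicity entry in 15.17 is specific neither to warfarin nor to dose. Patients also have history and exam visits on Days 8, 15 and 22. All of this limits the importance of the point. None of it supplies a required INR at the higher doses.

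**Conclusion.** The concern holds. For a warfarin patient who is stable at baseline and in range at the Day 2 to 8 check, table 4.1 and footnote 13 require no INR for the next 21 to 27 days (18 to 30 with the visit window). Those days include 13 or 14 of the 14 planned cycle 1 doses above 80 mg, and also the 7-day break. The count assumes full escalation on schedule and no additional testing under 3.18, the package inserts or local practice.

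Footnote 13 names no cycle. If Day 5 applies in every cycle, the gap is confined to cycle 1. If it applies only in cycle 1, the required INRs from cycle 2 onward are all pre-cycle values.

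The documents give no relation between regorafenib exposure and INR and no count of warfarin patients, so the size of the risk is unknown. The change is worth making because the hazard is recognised and the remedy is cheap. It has no bearing on the overall survival analysis.

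**What to change.** Amend footnote 13 of section 4.1 for patients on warfarin as follows:
- Keep the Day 5 (± 3) check, which covers 80 mg.
- Add INR at the existing cycle 1 Day 15 and Day 22 visits, about one week after the steps to 120 and 160 mg.
- Name the cycle or cycles to which Day 5 applies.
- State that the dose to be modified for a high value is the warfarin dose; the footnote does not say which drug it means.
- Cross-refer to the weekly monitoring note in 3.18 and say how long it applies once regorafenib has started.

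The cost is footnote wording plus about two INR tests per warfarin patient, with no new visits. Cycle 1 Day 15 already has chemistry and the STC1 blood draw, and Day 22 already has a history and exam.

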4.2 Treatment with anti-EGFR mAb (cetuximab or panitumumab) ± irinotecan

NOTE: Subjects should follow this test table while taking anti-EGFR mAb (cetuximab or panitumumab) ± irinotecan regardless of treatment arm.

Tests and procedures	≤7 days prior to randomization	Active Monitoring Phase							
		Cycle 1		Cycle 2		Prior to dosing each cycle beginning cycle 3+ (+/- 7 days)	Prior to dosing at restaging (C3 and every other cycle after) until progression (+/- 7 days)	Day 15 (While on anti-EGFR mAb +/- irinotecan)	End of Initial Treatment Mandatory Sequential Registration (if anti-EGFR mAb +/- irinotecan is initial treatment) ¹¹
		Week 1 (Day 1)	Week 3 (Day 15)	Week 1 (Day 1)	Week 3 (Day 15)				
History and exam, weight, ECOG PS, blood pressure	X	X ⁶	X	X	X	X			X
Height	X								
Adverse event assessment	X		X		X	X			X
Hematology ⁴ : CBC/ differential, ANC, INR/PTT ¹²	X	X ⁸	X	X	X	X		X	

Chemistry ⁴ : SGOT (AST), alk phos, T. bili, serum creatinine, calcium, glucose, Na, K, SGPT (ALT), Mg	X	X ⁸	X	X	X	X		X	Ar	
Albumin ⁴	X	X ⁸		X		X				
Tumor Blood Bio-Markers (CEA)	X			X			X			
Tumor measurement ¹ (CT scan of chest, abdomen and pelvis), CT component of a PET/CT, (MRI if CT is not feasible)	X						X			X ⁵
ECG ³	X									
Serum pregnancy test ²	X	X ⁸								
Mandatory blood sample-plasma ^{9, R}		X		X						
STC1 Biomarker blood collection		X	X							
Mandatory tissue sample-archival tumor paraffin(see Section 17.0) ^{7, R}		X						X		
Optional Blood sample -cfDNA Guardant 360 ^{9,10, R}										X

1. CT scans preferred (MRI if CT is not feasible), CT component of a PET/CT, of the chest, abdomen and pelvis. Use same imaging throughout the study. Tumor measurements at baseline (≤ 28 days prior to randomization) and every 8 weeks beginning on cycle 3 day 1 prior to treatment until progression.
2. For women of childbearing potential only.

3. Performed at screening and then as needed.
4. Hematology and chemistry tests to be done prior to each cycle.
5. If patient goes off study during Cycle 1 and last CT scan was done >28 days prior, the CT scan must be done.
6. If baseline history, exam, weight, ECOG PS, and blood pressure were performed \leq 3 days of C1D1, they do not need to be repeated for C1D1.
7. Receipt of archival tumor tissue is not required for study randomization and initiation of therapy. However, it is mandatory to receive the required tissue \leq 90 days from randomization. See section 17.0.
8. If screening tests occur \leq 7 days prior to C1D1, they do not have to be repeated prior to dosing.
9. Kits are required for this collection. Refer to Section 14.0.
10. Patients have the option to complete cfDNA testing at study completion and will be allowed to register with protocol ACCRU-GI-1611. Site will access results by creating an account at [REDACTED] Sites will be notified by Guardant Health via email when results are available in the portal. Refer to Section 13.7. See detailed instructions on the ACCRU website under Manuals and Forms.
11. At the time of disease progression or intolerance from initial treatment, patients will be re-registered (See 6.3) to Sequential Treatment Phase. Tests should be completed after re-registration and prior to dosing of sequential treatment. Patients will then move to the regorafenib test table (4.1).
12. If the INR/PTT is normal at screening (and subject is not on warfarin) this test will not need to be repeated unless indicated per investigator assessment. If a subject is on warfarin with stable INR/PT at baseline, the INR/PT should be assessed on Day 5 (+/- 3 days). If value is above the therapeutic range, the dose should be modified and the assessment should be repeated weekly until it is stable.

R Research funded.

5.0 Stratification and Grouping Factors:**5.1 Stratification Factors**

- 5.11 Prior bevacizumab treatment in the metastatic setting: yes vs no.
- 5.13 Treating physician decision on using Irinotecan with anti-EGFR mAb for this study: yes vs no.

5.2 Grouping Factors

- 5.21 Initial Treatment Received: Regorafenib vs. Anti-EGFR

6.0 Randomization Procedures**6.1 Site Procedures**

- 6.11 Study staff will need to complete the required training prior to gaining access to the registration application. This is located on the ACCRU webpage at [REDACTED] Refer to Study Resources→ Applications. Near the bottom of the page there will be a link to the “Research Registration Application Training.” After training is complete, study staff must complete the “Attestation of Training” and send to the ACCRU Registration Office at [REDACTED]
- 6.12 Documentation of IRB approval must be on file in the Registration Office before an investigator may register any patients. Approvals should be uploaded using the online ACCRU Regulatory Management System (ARMS).

In addition to submitting initial IRB approval documents, ongoing IRB approval documentation must be on file (no less than annually) with ACCRU. Approvals should be uploaded using the online ACCRU Regulatory Management System (ARMS). If the necessary documentation is not submitted in advance of attempting patient registration, the randomization will not be accepted and the patient may not be enrolled in the protocol until the situation is resolved.

Submission of annual IRB approvals is required until the study has been closed through your IRB.

